2.4 Study Rationale

Daré Biosciences Inc. is developing an intravaginal ring (IVR) to provide local administration of 17β -estradiol and natural progesterone to treat VMS in women with an intact uterus, while aiming to reduce the likelihood of the development of genitourinary symptoms. Non-oral routes such as vaginal administration should bypass the first-pass hepatic effect, although this has not been demonstrated conclusively. Among the various vaginal dosing treatment modalities, evidence suggests a patient preference for the use of IVRs over cream or tablets, with an improvement in adherence to treatment (Suckling J, et al., 2006). With low-dose estradiol IVRs already approved in the United States for the treatment of VMS due to menopause, and vaginal progesterone products also on the market, coadministration of the two hormones together in the same IVR is an attractive patient convenience proposition for the treatment of VMS and urogenital symptoms of menopause.

2.4.1 Dose Rationale

Estradiol and progesterone have been administered via IVR in previous studies (Hamada et al, 2003) however, the DARE-HRT1 17β -estradiol and progesterone IVR has not yet been tested in human subjects.

Estradiol – Pharmacokinetics of Vaginal Route

In a randomized clinical study with a novel vaginal capsule containing solubilised 17β -estradiol, the bioavailability and PK of the vaginal capsule in healthy postmenopausal women were compared to those of an approved vaginal estradiol tablet (Vagifem[®]) (Pickar JH, et al., 2016). A crossover design was used, with subjects randomized to receive single doses of novel capsule then the Vagifem tablet, or the Vagifem tablet followed by the novel capsule. Treatments were administered by an investigator. Blood samples were collected at intervals over 24 hours after treatment. Two separate studies investigated 10 μ g and 25 μ g doses.

CONFIDENTIAL

Mean values of PK parameters observed for both estradiol doses following single administration of the two treatments are provided in [Table 2.1](#). The C_{max} values for estradiol differed significantly between the two different formulations, with greater C_{max} values observed with the Vagifem tablets than the novel capsule. Similarly, AUC_{0-24} values were greater with the Vagifem tablet. This study also showed that the time to reach the highest observed (peak) concentration in plasma following administration (t_{max}) for vaginally administered estradiol is greatly dependent on the formulation.

Table 2.1 Mean Pharmacokinetic Values for Estradiol

| Dose (μg) | AUC_{0-24} (pg•h/mL) | | | C_{max} (pg/mL) | | | t_{max} (h) | |
|---------------------------|------------------------|----------------------|---------|-------------------|----------------------|---------|---------------|----------------------|
| | Test | Vagifem [®] | p | Test | Vagifem [®] | p | Test | Vagifem [®] |
| 10 | 49.62 | 132.92 | <0.0001 | 14.38 | 20.38 | 0.0194 | 1.75 | 9.28 |
| 25 | 89.21 | 292.1 | <0.0001 | 23.08 | 42.70 | <0.0001 | 1.85 | 11.18 |

p-values indicate statistical significance at <0.05 between the test products and the Vagifem products.

Source: [Pickar JH, et al., 2016](#)

Prescribing information for the FDA-approved IVR Femring reports PK data for estradiol ([FEMRING Package Insert, 2018](#)). Femring is a cured silicone elastomer IVR that releases estradiol acetate at two strengths: 0.05 mg/day and 0.10 mg/day, for 3 months. With the 0.05 mg/day IVR, the reported C_{max} was 1129 pg/mL, C_{avg} was 40.6 pg/mL, and the t_{max} was 0.9 hours. With the 0.10 mg/day IVR, the reported C_{max} was 1665 pg/mL, C_{avg} was 76.0 pg/mL, and the t_{max} was 0.7 hours.

Since the DARE-HRT1 IVR comprises an EVA polymer compared to Femring's silicone elastomer, predictions of PK that might be expected with the DARE-HRT1 based on the Femring data should be considered cautiously. Furthermore, the doses of estradiol in the Femring (50 and 100 $\mu\text{g}/\text{day}$) are not the same as those in the DARE-HRT1 IVR (80 and 160 $\mu\text{g}/\text{day}$). However, the estradiol PK results from DARE-HRT1 are expected within the same order of magnitude as those reported for Femring.

Progesterone – Pharmacokinetics of Vaginal Route

In a study comparing the PK of progesterone from a vaginal progesterone gel (Crinone 8%, 90 mg) with that of orally administered progesterone (Prometrium 100 mg), 12 healthy postmenopausal women were randomized in a 1:1 fashion to receive a single dose of the allocated progesterone treatment. The vaginally-administered progesterone had greater bioavailability than the oral progesterone in terms of AUC_{0-24} (1.48 ng•h/mL per mg versus 0.035 ng•h/mL per mg), with a correspondingly greater C_{max} (10.51 ng/mL versus 2.20 ng/mL). However, t_{max} was observed earlier with oral progesterone (1.00 hours) than with the vaginal gel (7.67 hours) ([Levine H, et al., 2000](#)).

The PK of vaginally administered progesterone has also been compared to that of intramuscular progesterone administration ([Miles RA, et al., 1994](#)) in a study with functionally agonadal women aged 25 to 54 years. Subjects were randomized to receive a cycle of estrogen and

progesterone replacement, comprising oral ethinyl estradiol with either vaginally administered micronized progesterone capsules (200 mg every 6 hours) or intramuscular progesterone (50 mg twice daily) from Day 15 of the cycle. For the PK assessments, samples were collected for 6 hours after the first progesterone dose, with samples for steady-state PK collected on Day 21. Single-dose exposure was significantly greater with the intramuscular treatment (C_{max} 16.06 ng/mL) than with the vaginal capsule (C_{max} 6.64 ng/mL), with a similar difference observed in steady-state concentrations (69.80 versus 11.90 ng/mL). Serum concentrations increased more rapidly with the intramuscular treatment than with the vaginal treatment. As expected, evaluation of progesterone levels in endometrial samples collected on Day 21 showed higher progesterone concentrations with vaginal treatment (11.50 ng/mL) than with intramuscular treatment (1.40 ng/mL).

An alternative vaginal progesterone formulation, using an effervescent delivery system rather than micronized progesterone capsules, showed similar results. Treatment with the effervescent delivery system was able to produce greater endometrial progesterone concentrations than the intramuscular treatment, while measured systemic exposure was lower (Paulson RJ, et al., 2014).

Another study compared progesterone PK following vaginal administration of two different formulations, both of which contained 100 mg progesterone. Single administrations of vaginal tablets (Endometrin[®]) and vaginal capsules (Utrogestan[®]) in postmenopausal women showed largely similar results for the two formulations. The AUC was 379.99 nmol/h/L with the tablet and 325.89 nmol/h/L with the capsule. A significant difference was observed for C_{max} of the two formulations, with values of 31.53 nmol/L reported for the tablet and 23.85 nmol/L for the capsule. The authors also reported an increase in systemic progesterone levels when subjects were “primed” with estrogen (3 mg/day ethinyl estradiol for 2 weeks) before receiving the progesterone treatment (Levy T, et al., 2000).

It is not clear how the PK of progesterone from the treatment modalities described here will compare with PK of progesterone released from the EVA ring of DARE-HRT1. It is clear though, that administration via the vaginal route should avoid a first-pass effect of liver metabolism, (Levy T, et al., 2000), which is supported by the comparison of the oral and vaginal routes described by Levine H, et al (2000).

2.4.2 Study Design Rationale

A parallel group study of DARE-HRT1 in healthy postmenopausal women is an appropriate design to assess PK and safety.

2.5 Hypotheses

No formal hypotheses will be tested.

CONFIDENTIAL

3 OBJECTIVES

3.1 Primary Objective

- To describe the PK parameters over 28 days of two different dose combinations of DARE-HRT1 intravaginal ring (IVR):
 - Estradiol 80 µg/progesterone 4 mg/day IVR
 - Estradiol 160 µg/progesterone 8 mg/day IVR

3.2 Secondary Objectives

- To assess the safety and tolerability of DARE-HRT1
- To compare the systemic exposure of estradiol, estrone, and progesterone over 28 days after administration of DARE-HRT1 IVR and once daily oral Estrace[®]/Prometrium[®]

3.3 Exploratory Objective

- To assess usability and subject tolerability of the DARE-HRT1 IVR

4 STUDY DESIGN

4.1 Study Design and Overview

This is a randomized, open-label, 3-arm, parallel group study in approximately 30 healthy postmenopausal women with intact uteri.

This study is designed to assess the PK of estradiol, estrone, and progesterone from DARE-HRT1 intravaginal rings at two dose strengths. Oral estradiol 1 mg/progesterone 100 mg once-daily for 28 days will serve as an active reference.

Three treatment groups will be assessed in this study as shown in [Table 4.1](#).

Table 4.1 Treatment Allocations

| Treatment Group and Number of Subjects | Treatment |
|--|--|
| IVR Dose 1 (n=10) | 28-day intravaginal ring 80/4 (estradiol 80 µg/day + progesterone 4 mg/day) |
| IVR Dose 2 (n=10) | 28-day intravaginal ring 160/8 (estradiol 160 µg/day + progesterone 8 mg/day) |
| Oral Reference (n=10) | Oral Estrace/Prometrium QD for 29 days (estradiol 1 mg/progesterone 100 mg oral capsule) |

Subjects who have been on prior hormone replacement therapy (HRT) therapy will be required to have the following washout period prior to randomization (for subjects actively using HRT, washout may begin after their informed consent):

- 4 weeks or longer for prior transdermal estrogen alone or estrogen/progestogen products
- 8 weeks or longer for prior oral estrogen, oral estrogen/progestogen, or intrauterine progestogen therapy
- 3 months or longer for prior progestogen implants and estrogen alone injectable drug therapy
- 6 months or longer for prior estrogen pellet therapy or progestogen injectable drug therapy

Due to study enrollment goals and the length of the required washout period outlined above, patients who are currently on either injectable or pellet therapy at the time of presentation for screening consideration will not be enrolled.

Washout periods of 8 weeks will require that Screening not commence until 28 days prior to Day 1.

Upon completion of their screening procedures and confirmation of their eligibility (including an endometrial biopsy, cervical screening test [if needed], and transvaginal ultrasound), eligible subjects will be admitted to the clinical research unit (CRU) on Day -1. Randomization will

CONFIDENTIAL

occur prior to initiation of treatment. Subjects will be randomized in a 1:1:1 ratio to the treatment groups.

Day 1 is defined as the first day of treatment, i.e., the day the IVR is self-inserted by the subject. The same IVR is to remain intravaginal for 28 days, with removal of IVR in the CRU on the morning of Day 29. For those randomized to the oral arm (Estrace/Prometrium), dosing will also begin on Day 1, concluding with a last dose on Day 29. Subjects in the oral arm will be directed to self-administer the medication in the morning with a meal and approximately 240 mL of water, starting on Day 2 through Day 27. Doses will be administered in the CRU each of the mornings of Day 1 and Days 28 and 29 with a moderate-fat breakfast.

Safety and tolerability assessments will include monitoring of adverse events and concomitant medications, clinical laboratory findings, physical examinations, vital signs, pelvic examinations, completion of a Usability and Tolerability questionnaire, and vaginal pH and cytology. Refer to the Schedule of Assessments for each treatment arm in Table 1.1 and [Table 1.2](#) for specific details.

IVR Treatment Groups:

- A single predose blood draw for estradiol, estrone, and progesterone will be obtained at screening and Day -1, and -1, -0.5, and 0 (immediately prior to insertion of IVR \pm 5 min) hours on Day 1. Plasma samples for estradiol, estrone, and progesterone will then be obtained at 0.5, 1, 2, 4, 8, 12, 24, and 48 hours following administration/insertion. Subjects will then be discharged from the CRU after safety assessments have been completed on Day 3.
- Subjects will return on the morning of Days 8, 11, 15, and 22 for a single blood draw as well as safety assessments.
- Subjects will return to the CRU on Day 28 for a PK blood draw, safety assessments, confirmation of IVR placement, and to begin confinement. On the morning of Day 29 a PK blood sample will be collected. The IVR will then be removed and PK samples will be collected 0.5, 1, 2, 4, 8, 12, and 24 hours post-removal.

Additional details of sampling and safety assessment procedures are presented in the Schedule of Assessments and Procedures - IVR Treatment Arm in Table 1.1.

Oral Treatment Group:

- A single predose blood draw for estradiol, estrone, and progesterone will be obtained at screening and Day -1, and -1.0, -0.5, and 0.0 hours immediately prior to and at 0.25, 0.5, 1, 2, 4, 6, 8, 10, 12, and 24 hours after the first dose on Day 1. Following the 24-hour PK, subjects will be discharged and instructed to self-administer oral estradiol and progesterone treatments each morning, with food and approximately 240 mL of water, at approximately the same time.

CONFIDENTIAL

- Subjects will return on Days 8, 15, and 22 for a single blood draw as well as safety assessments.
- Subjects will return to the clinic and be admitted on Day 28 to consume their oral dose with breakfast. A PK sample will be collected just prior to the last oral dose on the morning of Day 29, with additional PK sampling performed at 0.25, 0.5, 1, 2, 4, 6, 8, 10, 12, and 24 hours postdose.

Additional details of sampling and safety assessment procedures are presented in the Schedule of Assessments and Procedures - Oral Treatment Arm in Table 1.2.

4.1.1 Duration of Study

Subject participation is expected to last up to 65 days, including a 28-day screening period, a 30-day on-study period (consisting of a 29-day treatment period and additional sample collections), and the follow-up phone call 7 days after the last dose of the investigational product [IP]).

4.1.2 Definition of Study Completion

End-of-study procedures will be performed as specified in the schedule of assessments (Table 1.1 and Table 1.2). Subjects who terminate from the study early will have EOS procedures performed at the time of discontinuation. Subjects with ongoing significant clinical or laboratory findings will be followed until the finding is resolved or medically stable. All reasonable attempts will be made to follow-up with subjects. The subject's participation in the study will end once all study assessments and follow-up have been completed.

4.1.3 End of Study

The end of the study is defined as the date when the last subject has completed all study procedures up to and including the EOS/early termination visit as specified in the schedule of assessments (Table 1.1 and Table 1.2).

CONFIDENTIAL

5 SELECTION AND WITHDRAWAL OF SUBJECTS

Subjects must meet all the following criteria in order to be enrolled in the study.

5.1 Inclusion Criteria

Subjects must meet all inclusion criteria to be eligible for study participation.

1. Postmenopausal women with a body mass index (BMI) ≥ 18 and ≤ 38 kg/m².

$$\text{BMI} = \text{weight (kg)} / (\text{height [m]})^2$$

Postmenopausal is defined as 12-months of spontaneous amenorrhea or 6 months of spontaneous amenorrhea with serum FSH levels > 40 mIU/mL or 6 weeks postsurgical bilateral oophorectomy with or without hysterectomy (although subjects who have had a hysterectomy are not eligible for this study).

2. Normal cervix and vagina based on pelvic examination with speculum
3. An intact uterus
4. An acceptable result from an evaluable screening endometrial biopsy, evaluated by a pathologist. Tissue must be read as benign, inactive, or atrophic endometrium by at least one pathologist. If no tissue is obtained from the biopsy, the subject will be excluded.
5. Current on all Australian screening requirements for cervical cancer
6. Able and willing to correctly and independently complete all study procedures
7. Able to read, understand, and provide written informed consent after the nature of the study has been fully explained and must be willing to comply with all study requirements and procedures
8. Normal mammogram report within 24 months of screening

5.2 Exclusion Criteria

Subjects will not be eligible for study participation if they meet any of the exclusion criteria, or will be discontinued at the discretion of the investigator in consultation with the medical monitor if they develop any of the exclusion criteria during the study.

1. Prior abnormal cervical screening test (CST) or Pap result within 2 years of screening. Subject can have atypical squamous cells of undetermined significance (ASCUS), if HPV negative.
2. Subjects with any self-reported active sexually transmitted disease and/or evidence of infection based on visual vaginal exam by the investigator
3. Subjects with a UTI during screening as assessed by urine dipstick test with abnormal test findings (any positive result for leukocytes AND any positive result for nitrites)
4. Subjects with > 4 mm endometrium lining at screening (on the transvaginal ultrasound)

CONFIDENTIAL

5. Have a history of endometrial hyperplasia or cervical or uterine carcinoma
6. Subjects with indwelling catheters or requiring intermittent catheterization
7. Subjects with multiple or unsuccessful (e.g., still having symptoms) pelvic reconstructive surgery, or suffers from pelvic relaxation
8. Subjects who have had a hysterectomy
9. Subjects taking any estrogen and/or progesterone products (see Section 4.1 for washout requirements)
10. Subjects with concomitant use of personal lubricants (water-based lubricants are allowed) or any intravaginal product or medication, either by prescription or over-the-counter (e.g., Femring [estradiol acetate vaginal ring], ESTRING[®] [estradiol vaginal ring]) with the exception of those who agree not to use these products during the IVR use period
11. Self-reported or observed vaginal irritation; vaginal, vulvar, or cervical lesions, undiagnosed vaginal bleeding; or tenderness
12. Subjects with a finding of clinically significant uterine fibroids at screening
13. Subjects with a known hypersensitivity to progesterone, estradiol, Femring, or the components of the IVR (e.g., ethylene vinyl acetate)
14. Subjects with known hypersensitivity to peanuts (Prometrium capsules contain peanut oil)
15. Subjects with prior pelvic malignancies
16. Subjects with a history of any severe acute or chronic medical or psychiatric condition or laboratory abnormality that could increase the risk associated with trial participation or study treatment administration or could interfere with the interpretation of trial results and, in the judgment of the investigator, would make the subject inappropriate for entry into the trial. This includes but is not limited to the following:
 - a. Human immunodeficiency virus (HIV) infection (confirmed by medical history/serology testing)
 - b. Active chronic hepatitis B or hepatitis C infection including hepatitis B surface antigen and hepatitis C antigen positive subjects with or without abnormal liver enzymes (confirmed by medical history/serology testing)
 - c. Concurrent neurodegenerative disease
 - d. Cardiovascular: uncontrolled hypertension, unstable angina, myocardial infarction or symptomatic congestive heart failure within the past 6 months, serious uncontrolled cardiac arrhythmia, use of Class 1 antiarrhythmic medications, or history of venous thromboembolism or stroke
 - e. Dementia or significantly altered mental status that would prohibit the understanding or rendering of informed consent and compliance with the requirements of the protocol
 - f. History of gallbladder disease unless gallbladder removed

CONFIDENTIAL

g. Symptomatic bacterial vaginosis

17. Have fasting triglyceride of > 300 mg/dL and/or total cholesterol of > 300 mg/dL
18. AST or ALT > 1.5 times the upper limit of normal
19. Fasting glucose > 125 mg/dL
20. Evidence of current alcohol or drug abuse in the past 60 days including a positive result from the urine drugs of abuse or alcohol screen, or history of drug or alcohol dependence in the last two years, as assessed by principal investigator. Alcohol abuse is defined as greater than 14 standard units/week for females and drug abuse is defined as known psychiatric or substance abuse disorder that would interfere with participation with the requirements of this study, including current use of any illicit drugs.
21. Participation in any other investigational drug or device trial in which administration of an investigational study drug/device occurred within 30 days or placement of a non-drug eluting medical device within 15 days prior to screening.

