6.7 Concomitant Medications and Procedures and Other Restrictions

6.7.1 Concomitant Medications and Procedures

No concomitant medications and personal lubricants (water-based lubricants are allowed) or any intravaginal product or medications (prescription, OTC, and herbal), with the exception of paracetamol 650 mg/day (not to exceed 2000 mg total in the 7 days prior to administration of the study drugs), or vaccinations may be administered during the study unless they are prescribed by

CONFIDENTIAL

the investigator for treatment of specific clinical events. No concomitant procedures will be performed during the study unless approved by the investigator. All medications (prescription and OTC), vitamin and mineral supplements, and herbs taken during the study will be documented on the concomitant medication eCRF. Information recorded will include: start and stop dates and times, dose and route of administration, and indication. Medications taken for a procedure will also be included, as well as the procedure itself.

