7.4.2 Pharmacokinetic Parameters

Pharmacokinetic variables will be calculated from the plasma concentration data using noncompartmental methods (Phoenix™ WinNonlin®, Version 6.4 or later; Certara LP, Princeton, New Jersey, USA) and actual sampling times.

The following PK parameters will be determined:

| | |
|-----------|--|
| C_{avg} | Time-weighted average observed plasma concentration over 24 hours (Day 29 PK profile for oral dosing only) |
| C_{ss} | Steady-state concentration (IVR dosing only) |
| C_{max} | Maximum observed plasma concentration |
| C_{tau} | Concentration at the end of the dosing interval (tau) (oral dosing only) |
| t_{max} | The time that C_{max} was observed |

CONFIDENTIAL

| | |
|----------------|---|
| AUC_{0-24} | Area under the plasma concentration-time curve from time 0 to 24 hours; calculated using the linear/log trapezoid rule (oral dosing only) |
| AUC_{D1-D30} | Area under the plasma concentration-time curve from time 0 (Day 1) to the time of the last quantifiable concentration on Day 30; calculated using the linear/log trapezoid rule (IVR dosing only) |
| $t_{1/2,eff}$ | Effective half-life; calculated using AUC_{0-24} on Days 1 and 29 (oral dosing only) |

Baseline correction, using the average of the three predose concentrations on Day 1, may be performed prior to the calculation of PK parameters by noncompartmental methods. C_{max} (and t_{max}) will be computed over each 24-hour PK profile (Days 1 and 29) and, for IVR administration, over the entire 28-day treatment interval. Additional PK parameters may be calculated as appropriate.

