9.5 Pharmacokinetic Statistical Analysis

The DARE-HRT1 IVR is the test (investigational) product of interest, with two dose combinations of estradiol and progesterone being assessed. Thus, comparisons of the estrogen and progesterone concentrations will be made for each dose combination as DARE-HRT1 IVR versus oral therapy.

The PK analysis will be performed for each IVR dose and assessed versus the oral reference. Graphics will be provided to allow for visual inspection of the mean and individual subject concentration-time profiles.

The PK parameters C_{avg} , C_{ss} , C_{max} , C_{tau} , t_{max} , AUC_{0-24} , AUC_{D1-D30} , and $t_{1/2, eff}$ will be determined from the plasma concentration-time profiles, where possible. Geometric mean values and coefficients of variation (CV%) will be estimated and reported.

If possible, the dose proportionality for the DARE-HRT1 IVR estradiol and progesterone doses will be assessed.

Other details of the PK analysis will be described in a separate Statistical Analysis Plan.

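### No minimum time off vaginal estrogen or progestogen is set before the Day 1 baseline; with the optional baseline correction, leftover hormone would lower a recent user's Css

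*Combined protocol and SAP*

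**What the plan says.** Section 4.1 sets the general rule: "Subjects who have been on prior hormone replacement therapy (HRT) therapy will be required to have the following washout period prior to randomization". The list that follows starts with "4 weeks or longer for prior transdermal estrogen alone or estrogen/progestogen products" and goes on to 8 weeks for oral and intrauterine products, 3 months for progestogen implants and estrogen injectables, and 6 months for estrogen pellets and progestogen injectables. No line covers a vaginal ring, cream, insert, tablet or gel.

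Section 5.2 opens with "Subjects will not be eligible for study participation if they meet any of the exclusion criteria", so one criterion is enough to exclude. Criterion 9 excludes "Subjects taking any estrogen and/or progesterone products (see Section 4.1 for washout requirements"), which sends the reader back to 4.1 for timing. Criterion 10 excludes users of intravaginal products, gives Femring and ESTRING as examples, and ends "with the exception of those who agree not to use these products during the IVR use period".

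Section 6.7.1 prohibits, in all arms during the study, "No concomitant medications and personal lubricants (water-based lubricants are allowed) or any intravaginal product or medications (prescription, OTC, and herbal").

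On analysis, section 7.4.2 says: "Baseline correction, using the average of the three predose concentrations on Day 1, may be performed". Css and Cmax of estradiol, estrone and progesterone are the primary endpoints (9.4.1). Section 9.5 adds: "Other details of the PK analysis will be described in a separate Statistical Analysis Plan".

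**The concern.** The trial measures plasma estradiol, estrone and progesterone from a vaginal ring, and the vaginal route is the one route with no washout. Criterion 9 borrows its timing from a list that is silent here. The criterion 10 exception names two estradiol products and ties abstinence to a period that is undefined, most naturally starts at insertion, and has no meaning in the oral arm. For vaginal estradiol the two criteria pull in different directions.

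The practical gap is the woman who stopped a vaginal hormone shortly before Day 1. PK samples are drawn at Screening and Day -1 and could show a raised or falling level, but no eligibility or baseline rule uses them. The PK Population in 9.2 has no condition on prior medication. At stake is a primary endpoint in an arm of 10, if the predose mean is subtracted.

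**Working it through.** **Direction.** Let E be the endogenous level, S the study ring's contribution and R(t) the residue of the old product at time t.

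Corrected value = [E + R(t) + S] - [E + R(0)] = S - [R(0) - R(t)].

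If the residue decays, R(t) is below R(0), the error is negative, and it approaches -R(0). The protocol does not say which days Css uses, but the sign is the same for any on-treatment window. Without correction the error is +R(t), which is small by the time of steady state; only early Day 1 levels would be noticeably raised.

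**Inputs from section 2.4.1.** Femring 0.05 mg/day: Cavg 40.6 pg/mL. Femring 0.10 mg/day: Cavg 76.0 pg/mL. Vagifem AUC over 24 h (Table 2.1): 132.92 pg·h/mL for 10 µg and 292.1 for 25 µg, so average levels of 132.92/24 = 5.5 and 292.1/24 = 12.2 pg/mL.

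**Assumptions.**
- Study ring Css by dose-scaling Femring. For 80 µg: 80 × 40.6/50 = 65.0 and 80 × 76.0/100 = 60.8; use 63. For 160 µg: 129.9 and 121.6; use 126. Section 2.4.1 itself urges caution with Femring-based predictions.
- Residue at the Day 1 baseline of 5% to 25% of the old product's average level. This range is chosen, not derived. Under exponential decay, 25% corresponds to two half-lives off product.
- One affected woman among 10, correction applied, residue gone by steady state.

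**Formulas.** Her corrected fraction is f = 1 - residue × old level / Css. The fall in the arm's geometric mean is 1 - f^(1/10).

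| Prior product, 80/4 arm (Css 63) | Residue | f | Her Css falls | Arm mean falls |
|---|---|---|---|---|
| Femring 0.05 | 5% | 0.968 | 3.2% | 0.3% |
| Femring 0.05 | 10% | 0.936 | 6.4% | 0.7% |
| Femring 0.05 | 25% | 0.839 | 16.1% | 1.7% |
| Femring 0.10 | 5% | 0.940 | 6.0% | 0.6% |
| Femring 0.10 | 10% | 0.879 | 12.1% | 1.3% |
| Femring 0.10 | 25% | 0.698 | 30.2% | 3.5% |

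**Sensitivity.**
- Vaginal tablets at 10% to 25% residue: arm mean falls 0.1% to 0.2% (10 µg) and 0.2% to 0.5% (25 µg).
- Femring 0.05 with Css 40 instead of 63: 1.1% at 10% residue, 2.9% at 25%. With Css 100: 0.4% and 1.1%.
- 160/8 arm (Css 126), Femring 0.05: 0.3% at 10%, 0.8% at 25%.
- Spread, for an assumed geometric CV of 40%: log variance ln(1 + 0.4²) + (ln 0.839)²/10 = 0.1484 + 0.0031 = 0.1515, so the CV becomes 40.4%.
- Time since stopping, Femring 0.05, assumed residue half-life 0.5 to 3 days: stopping 1 day before Day 1 leaves 10 to 32 pg/mL and lowers her own Css by about 16% to 51%; stopping 7 days before lowers it by 0% to 13%. A 50% fall in one woman moves the arm mean by 1 - 0.5^(1/10), about 7%.

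The documents give neither a half-life after removal nor the number of such women. They give no level for ESTRING. Progesterone is not quantified, because section 2.4.1 says its PK from the EVA ring cannot be inferred from the vaginal products it reviews.

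**The case against.** The strongest reply is that other rules already cover most of the gap. Criterion 9 excludes anyone on an estrogen or progesterone product, and eligibility is checked again at Day 1 predose (Tables 1.1 and 1.2). Section 6.7.1 bans intravaginal products in every arm. Its paracetamol allowance is counted over the week before dosing, which suggests that the ban applies before Day 1; section 4.1.1 counts screening as part of participation. On that reading, a woman who used a vaginal hormone during screening took a prohibited medication, which 11.1.1 lists as a deviation. The harm also needs several things at once: a recent user, a higher-dose product, persisting residue, allocation to a ring arm, and use of an optional correction whose details are deferred.

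Most of this stands, and it rules out two stronger readings. A reader might infer from criterion 10 that a woman may keep using Femring until the study ring goes in; criterion 9 bars her regardless of the exception. A reader might also infer that a woman who stopped days before Day 1 satisfies every rule and could never be a deviation; 6.7.1 can be read to reach the period before dosing, so the documents do not support a statement that firm.

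What the reply does not do is supply a washout. A ban during the study sets no interval off product. The screening window runs from Day -28 to Day -2, so an individual's screening can be short. And 4.1 lets women on active HRT begin washout after consent, so the protocol itself relies on the 4.1 list, not on 6.7.1, to fix the time off hormone.

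**Conclusion.** The concern holds in a limited form. The washout list omits vaginal estrogen and progestogen, criterion 9 depends on that list, and criterion 10 names two estradiol rings in an exception that gives no time off before Day 1. Where the baseline correction is applied, decaying residue biases the affected woman's Css downward. The direction is certain under that condition; the size is not.

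For one woman in 10 and 5% to 25% residue of a Femring-type ring, the 80/4 geometric mean estradiol Css falls about 0.3% to 3.5%. The effect is smaller in the 160/8 arm and for tablets, and larger only if she stopped within a day or so or the residue clears slowly. It would be tempting to conclude that the primary endpoint is biased. The documents do not show that: the correction is optional, no such woman is known to enrol, the trial is descriptive with no formal hypotheses, and without correction the effect on Css is small. This is a worthwhile, inexpensive clarification.

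**What to change.** 1. Add a line to the section 4.1 washout list for prior vaginal estrogen or progestogen products (ring, cream, insert, tablet, gel). Four weeks would match the shortest interval already listed. The documents hold no data from which to derive a length, so the sponsor should confirm it.
2. Remove Femring and ESTRING from the criterion 10 exception, so that vaginal hormones fall only under criterion 9 and section 4.1.
3. Optional: state the criterion 10 abstinence period as Screening through Day 30 in all arms. This largely restates 6.7.1 but removes the undefined term.

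The cost is wording in two places, with no added visits, samples or subjects. The downside is that a few women start up to 4 weeks later.
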